
Also called Clinical Benefit Rate is defined as the proportion of subjects with CR or PR or Stable Disease (SD).

e) The duration of response and stable disease

The duration of response is calculated for only those patients who responded. It was the time from first objective response to first observed progression of disease or death if the death was due to disease progression (whichever comes first).

The duration of stable disease is calculated for only those patients who exhibited a best response of stable disease response as per RECIST v1.1. It is the time from first SD response to first observed progression of disease or death if the death was due to disease progression (whichever comes first).

The duration of response and stable disease will also be calculated for the patients who responded and/or had a best response of SD.

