10.2.2.3 Time to Progression (TTP) from Start of Sunitinib

TTP defined as time from Sunitinib Start Visit to date of first observed progression or date of death if the death was due to disease progression (whichever came first). Progressive disease is defined by RECIST v1.1 criteria and by clinical evaluation.

Note: For intermediate-risk patients included in the trial according to protocol versions before version Final 4.0, the first imaging assessment after nephrectomy will be used as baseline for evaluation of TTP, irrespective of whether or not the imaging assessment coincided with sunitinib treatment start. Further details will be provided in the SAP.

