12 STATISTICAL METHODS AND DETERMINATION OF SAMPLE SIZE

12.1 Statistical and Analytical Plans

A separate SAP, which will provide the technical details of the statistical analysis outlined below, will be prepared and approved before study data analysis, including any interim analysis.

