12.1.2 Definitions

For definitions used for endpoint evaluation, see *Section 10.2.1* and *Section 10.2.2*.

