Proportion of ORR from start of sunitinib treatment will be derived as the proportion of patients with the individual's best overall response scored as "CR" or "PR" (using RECIST 1.1) across all time points from first visit six (6) weeks after sunitinib treatment, to end-of-study visit. Similarly, DCR will be derived as proportion of patients with best overall response scored as "CR", "PR" or "SD".

ORR and DCR will be summarised and comparison of treatment groups will be made using the Cochran Mantel-Haenzel test, adjusting for strata.

Duration of response will be derived only for patients meeting the ORR definition CR or PR, at least once, as the date of the first occurrence of PD or death minus the date at which the CR or PR was first observed, plus 1 day. Patients without an occurrence of a PD or death after CR or PR will contribute with the time up till last tumor assessment. Data will be summarised descriptively.

Duration of clinical benefit will be derived only for patients meeting the DCR definition CR, PR or SD at least once, as the date of the first occurrence of PD or death minus the date at which the CR, PR or SD was first observed, plus 1 day. Patients without an occurrence of a PD or death after CR, PR or SD will contribute with the time up till last tumor assessment. Data will be summarised descriptively.

The duration of stable disease is calculated for only those patients who exhibited a best response of stable disease response and will be calculated as the date for the first SD

response to the date of the first observed progression of disease or death before end of trial, if the death was due to disease progression (whichever comes first) plus 1 day. Data will be summarised descriptively.

Response rate from Sunitinib Start Visit

Evaluation of response rate, based on CT and according to the RECIST 1.1 guideline, from Sunitinib Start Visit will be based on the subpopulation from FAS who have been exposed to at least one dose of sunitinib. Number of patients with CR, PR, PD, and SD after start of sunitinib will be summarized using the underlying ordinal scale.

Waterfall charts will be used to display the percent change in target lesion tumour dimension vs best overall response and Two types of Swimmer plots will be created, one with bars showing time from randomization and one from sunitinib start. In these events for progressive disease, end of trial and vital status will be indicated.

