Response rate from Screening to Post-Nephrectomy

The evaluation of RECIST response rate between Screening and Post-Nephrectomy assessment will be summarised in the same way as described for response rate after Sunitinib Start Visit.

Time to tumor progression (TTP)

TTP from start of Sunitinib treatment will be derived as date for tumor progression, or clinical disease progression (other than RECIST 1.1) if occurring before tumor progression, minus date for start of sunitinib treatment plus 1 in the same way as done for PFS but excluding any deaths, if death before tumor or disease progression the subject will be censored at time of last CT during the trial. This variable will be analysed using the same method as for the evaluation of PFS.

Infiltrating CD8+ T-cells

The individual evaluation of intratumoral infiltration of CD8+ T-cells will be conducted as described in the protocol, where each patient will have the number of CD8+ T-cells/mm² counted from 3 areas in two separate biopsies by [REDACTED]. Each patients median of the 6 individual counts will be calculated. The patient median number of CD8+ T-cells will be summarised by treatment group, strata and overall using descriptive statistics for continuous data as described in Section 12.1.4.

At the GLP compliant laboratory [REDACTED] a validated automated quantification of intratumoral CD8+ T cells, using whole slide scanning instruments, will be performed. The tumoral area will be delineated by a trained operator and the surface of CD8+ labeling percentage will be assessed in the delineated areas. Each patients mean percentage from the two (2) primary tumor biopsies will be used for statistical evaluations. Patient's mean percentage will be evaluated for the treatment arms per stratum and in total using summary statistics, as described for continuous data in Section 6.3.2.

Relative number of tumor infiltrating CD8+ T-cells in the resected primary tumor compared to number of infiltrating CD8+ T-cells in available diagnostic pre-biopsy (sample from either primary tumor or metastasis), not be evaluated as described in the protocol due to missing pre-biopsy samples.

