14.2 EFFICACY DATA

(Efficacy presentations will be split by stratum, all presentation will be based on FAS if not otherwise stated below)

Tables

- 14.2.1 Life table statistics of OS by treatment group (FAS, PPS and Subgroups)
- 14.2.2 Quartile Estimates (Median) and Confidence Intervals for OS (FAS, PPS and Subgroups)
- 14.2.3 Log rank test compare survival functions for treatments groups OS (FAS, PPS and Subgroups)
- 14.2.4 The estimates of the second primary endpoint of the proportion of 18-months survival and corresponding z-test test. (FAS, PPS and Subgroup)

- 14.2.7 Life table statistics of PFS from start of Sunitinib by treatment group
- 14.2.8 Quartile Estimates (Median) and Confidence Intervals for PFS from start of Sunitinib (FAS and Subgroup)
- 14.2.9 Log-Rank test compare survival functions for treatment groups PFS from start of Sunitinib (FAS and Subgroup)
- 14.2.13 Summary of RECIST 1.1, Number of patients with CR, PR, PD, SD, and "Not Evaluable" by visit from Screening to Sunitinib Start Visit (FAS and Subgroup)
- 14.2.14 Summary of RECIST 1.1, Number of patients with CR, PR, PD, SD, and "Not Evaluable" by visit after Sunitinib Start Visit (FAS and Subgroup)
- 14.2.15 Summary of ORR and DCR from start of Sunitinib (FAS and Subgroup)
- 14.2.16 Cochran Mante -Haenze test for ORR and DCR (FAS and Subgroup)
- 14.2.17 Summary of duration of response, and duration of clinical benefit (FAS and Subgroup)
- 14.2.18 Summary of duration of stable disease (FAS and Subgroup)
- 14.2.19 Life table statistics of TTP from start of Sunitinib by treatment group (FAS and Subgroup)
- 14.2.20 Quartile Estimates (Median) and Confidence Intervals for TTP from start of Sunitinib (FAS and Subgroups)
- 14.2.21 Log-Rank test compare survival functions for treatment groups TTP from start of Sunitinib (FAS and Subgroups)
- 14.2.22 Summary of tumor infiltrating CD8+ T-cells and relative number of tumor infiltrating CD8+ T-cells, [REDACTED] and [REDACTED] (FAS and Subgroups)
- 14.2.23 Summary of ECOG performance by visit (FAS and Subgroups)
- 14.2.24 [REDACTED]
- 14.2.25 Summary of immunohistology parameters (CD8+ T-cells) in a biopsy from adjacent normal kidney tissue collected approximately 2 cm from the tumor margin and in a metastasis biopsy where applicable, [REDACTED] and [REDACTED] (FAS and Subgroups)

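### SAP drops progression deaths that the protocol counts as TTP events, and ends duration of response at deaths that the protocol does not count

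*SAP*

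**What the plan says.** **TTP.** Protocol 10.2.2.3 ends TTP at "date of first observed progression or date of death if the death was due to disease progression", whichever is first, and accepts progression by RECIST 1.1 or by clinical evaluation. SAP 6.3.6 also accepts clinical progression, but derives TTP "excluding any deaths, if death before tumor or disease progression the subject will be censored at time of last CT during the trial". Appendix 1 of the SAP plans a between-arm test on the result, table 14.2.21: "Log-Rank test compare survival functions for treatment groups TTP from start of Sunitinib".

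**Duration of response.** Protocol 10.2.2.2 says: "It was the time from first objective response to first observed progression of disease or death if the death was due to disease progression". SAP 6.3.6 uses "the date of the first occurrence of PD or death minus the date at which the CR or PR was first observed", plus one day, without a condition on cause and without a cut-off date. The SAP's duration of clinical benefit carries the same any-death rule.

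**Duration of stable disease.** Here the SAP keeps both limits: it ends at progression "or death before end of trial, if the death was due to disease progression".

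**Which document defines the endpoints.** Protocol 12.1.2 reads "For definitions used for endpoint evaluation, see" and points to Sections 10.2.1 and 10.2.2. Protocol 12.1 describes the SAP as the document "which will provide the technical details of the statistical analysis outlined below".

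**Declared changes.** SAP 6.1 lists changes to the planned analyses. None of its legible bullets mentions TTP or duration of response. Two bullets are redacted.

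**The concern.** The protocol fixes the events and leaves technical detail to the SAP, but the SAP changes the events. For TTP, a patient who dies of progression before any progression has been recorded is taken out of the risk set at the last scan, just when the disease has advanced most. That censoring is informative, and it acts on an endpoint with a planned log-rank test. Duration of response moves the opposite way, so one results section would leave progression deaths out of TTP and let unrelated deaths end a response. The stable-disease rule shows that the SAP can work with cause of death, so lack of data does not explain the difference.

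At stake are the within-arm TTP curves and medians, the meaning of the response durations, and a choice of event rule left open in an open-label trial whose data are reviewed as they accumulate (SAP 6.2).

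**Working it through.** The documents give no TTP or duration figure, so there is nothing to reproduce. The rules are compared first, then sized under stated assumptions.

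**1. Death rules side by side**

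| Endpoint | Protocol | SAP |
|---|---|---|
| TTP | Progression death is an event | No death is an event; censored at last CT |
| Duration of response | Progression death only | Any death, no cut-off |
| Duration of clinical benefit | Not defined under this name | Any death, no cut-off |
| Duration of stable disease | Progression death only | Progression death only, before end of trial |

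**2. Who is affected in TTP.** Only progression deaths with no earlier RECIST or clinical progression, because both documents count clinical progression.

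**3. Size of the TTP shift (illustration).** Assumptions: exponential failure with median 8 months (34.8 weeks); a share d of failures are such deaths; no dropout. Scans fall at weeks 6, 12, 24 and 36 after sunitinib start (protocol 7.2.1.6).

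- Weekly hazard: ln 2 / 34.8 = 0.0199. Survival over a 6-week gap is 0.887, over a 12-week gap 0.787.
- Protocol rule at week 36: 0.887² × 0.787² = 0.488.
- SAP rule: deaths within a gap leave the risk set at its start, so each gap with survival s contributes s / (1 − d(1 − s)). Multiply over two 6-week and two 12-week gaps.

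| d | 6-week factor | 12-week factor | SAP week 36 | Shift (points) |
|---|---|---|---|---|
| 5% | 0.892 | 0.796 | 50.4% | 1.6 |
| 10% | 0.897 | 0.804 | 52.1% | 3.3 |
| 20% | 0.908 | 0.822 | 55.7% | 6.9 |

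A simulation of 400,000 patients per setting agrees. For medians from 6 to 12 months the shifts are about 1.4 to 1.7, 2.8 to 3.4 and 5.9 to 7.3 points.

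**4. Against sampling error.** SE = √(0.488 × 0.512 / n): 5.3 points for n = 90, 6.5 for 60 and 9.1 for 30. Shares of 5% and 10% stay below one SE; 20% exceeds it for all 90 patients pooled.

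**5. Events lost.** With a last scan at week 65 (assumed, within the 61 to 70 weeks that the visit windows imply), 90 × (1 − e^(−0.0199 × 65)) ≈ 65 events. The SAP rule loses the fraction d: about 3, 7 or 13. SAP Section 5 uses the sunitinib-exposed subset; with an assumed 70 patients, about 2.5, 5 or 10 of 51 are lost.

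**6. Arm comparison.** The SAP rule multiplies each arm's event hazard by roughly 1 − d. Equal shares leave a null hazard ratio at 1.00. Shares of 5% and 15% give 0.85/0.95 = 0.89 or 0.95/0.85 = 1.12, depending on which arm has more.

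**7. Duration of response.** For an in-trial death not due to progression, the SAP uses the date of death, and the protocol rule would stop at the last scan. The two dates differ by at most one scan gap if no scan is missed: 12 weeks nominal, or 14 weeks from week 12 minus 7 days to week 24 plus 7 days. The direction depends on the summary. As plain durations, the SAP value is longer. In a Kaplan-Meier summary, counting the death as an event shortens the median, roughly by the factor 1 − r if a share r of the ending events are such deaths. The SAP says only that the data will be summarised descriptively. With no cut-off, the one-gap bound does not cover post-study deaths.

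**The case against.** The strongest reply is about weight. TTP and the durations are secondary, the trial is unpowered, and all testing is labelled exploratory. The affected group is residual, because clinical progression already counts and patients who respond inadequately are to have an End-of-Study Visit before they are withdrawn (protocol 9.6). No passage gives the share of progression deaths without earlier progression, so 20% is an assumption without support, and a simulation without dropout gives event counts at the upper end. Duration of response has no planned between-arm test. A TTP that ignores deaths is also coherent in itself. All of this stands and limits the size. It does not remove the conflict, since both event rules cannot be the analysis.

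Three stronger readings are tempting, and the documents do not support them.

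- *That the TTP comparison is biased between arms.* This needs unequal shares, and nothing in the documents shows them.
- *That the changes were made without declaration.* The two redacted bullets in SAP 6.1 leave this open.
- *That the PFS rule is unworkable because end-of-trial is undefined.* SAP usage points to the patient's own last visit: 6.3.5 contrasts deaths before end of trial with those found in the additional collection, and 6.6 uses the term for a withdrawing patient's visit. Protocol 7.5 defines a similar but different term, end of study, at trial level. One clarifying clause is enough. Censoring PFS on central RECIST assessment follows protocol 10.4.3 and is not at issue.

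**Conclusion.** The conflict is real and sits in the current text of both documents. As written, the SAP overstates within-arm TTP relative to the protocol's definition, and it applies a broader death rule to duration of response, and to duration of clinical benefit, than to duration of stable disease.

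The effect is minor to moderate, and its true size cannot be known from the documents. The calculated shifts rest on an assumed share, an exponential model and medians of 6 to 12 months. The direction for duration of response is not settled. This should be fixed before database lock, but it does not threaten the primary analyses.

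**What to change.** 1. **TTP.** Count death due to disease progression as an event at the date of death, as protocol 10.2.2.3 does, with the same death cut-off as PFS. State who assigns the cause and from what source, and sign off the list before database lock. Adverse event coding alone will not supply the cause, because protocol 11.2 bars progressive disease as a reported term; the terminal reports in protocol 11.3 are one possible source. Deaths of unknown cause are not events in the main run; one sensitivity run counts them as events. Alternatively, keep the SAP rule, declare and justify it in SAP 6.1, and run the protocol rule as a sensitivity analysis.
2. **Duration of response.** Use the protocol 10.2.2.2 death rule with the same death cut-off as duration of stable disease, and make duration of clinical benefit consistent with it, or declare the difference.
3. **PFS, clarification only.** Add one clause to SAP 6.3.6 saying whether end-of-trial means the patient's own last visit, and note the cut-off as a departure from protocol 10.2.2.1, which has none. No other change to PFS.

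The cost is SAP wording, one changed TTP derivation and a cause review of few deaths (about 3 to 13 in the illustration). The downside is that attributing deaths to progression takes judgement in an open-label trial, and estimated TTP may come out slightly shorter.

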7.2.1.6 SFU[6W], SFU[12W], SFU[24W], SFU[36W], SFU[48W], and SFU[60W]

These visits are applicable for all patients unless locally CT-verified PD occurs. In case of PD this visit should be considered the End-of-Study Visit.

If SFU[60W] is scheduled ≥ 76 weeks since Screening this visit should be considered the End-of-Study Visit, *Section 7.2.1.7*.

TIME WINDOWS:

SFU[6W]: 6 weeks (± 7 days) after Sun-Start Visit
SFU[12W]: 12 weeks (± 7 days) after Sun-Start Visit
SFU[24W]: 24 weeks (± 7 days) after Sun-Start Visit
SFU[36W]: 36 weeks (± 7 days) after Sun-Start Visit
SFU[48W]: 48 weeks (± 7 days) after Sun-Start Visit
SFU[60W]: 60 weeks (± 7 days) after Sun-Start Visit

NB: The CT/MRI scans do not have to be done the very same day as the corresponding study visits. However, each CT/MRI scan has to be done within the specified time window for the corresponding visit.

ACTIVITIES AND ASSESSMENTS:

The same activities and assessments will be done at these visits as was done on Sun-Start Visit except for auto- and alloimmunization, *Section 7.2.1.5*. In addition to dispense of sunitinib, the site personnel will collect unused and empty sunitinib packages (distributed at the previous visit) from the patient for drug accountability, *Section 9.1.4*.

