8.5 Removal of Patients from Therapy or Assessment

Patients are free to discontinue their participation in the study at any time. Withdrawal from the study will not affect or prejudice the patient's further care or treatment. Patients may be withdrawn from study treatment and assessments at any time, if deemed necessary by the Investigator.

Patients who discontinue treatment with Intuvax and/or sunitinib for safety reasons (including DLT, see *Section 11.5*) or due to concomitant medication (*Section 9.6*) will not necessarily be considered withdrawn from the study unless there are other reasons for withdrawal. They should return for all following visits and assessments until PD.

Examples of reasons for withdrawal of patients from this study are:

- Progressive disease on sunitinib treatment
- Screening failure
- The decision of a patient to withdraw from the study (i.e. if the patient withdraws informed consent)
- Administration of concomitant medication prohibited by this protocol, *Section 9.6*
- Pregnancy
- Patient is lost to follow-up
- RCC diagnosis is not confirmed by histological findings from the biopsy collected at nephrectomy or, if applicable, from confirmatory pre-study treatment diagnostic biopsy

The reason and date the patient is withdrawn from the study and subsequent planned replacement therapy will be documented in the electronic case report form (eCRF).

All patients that have received IMP must have safety evaluations for 30 days after the last dose of IMP, *Section 11.2*.

If a patient is withdrawn from further assessments, the Investigator should attempt to complete all discharge procedures, i.e. End-of Study Visit. All AEs should be followed up according to *Section 11.2*.

If a patient is withdrawn from the study, all data collected until the time of withdrawal will be used in the analyses.

Survival data (including post-study survival data if applicable) will be collected and analyzed for all patients withdrawn from the study, *Section 11.3*.

Patients randomized to Intuvax who withdraw from the study before administration of the first dose of Intuvax will be considered screening failures. Patients randomized to sunitinib alone who withdraw from the study before any assessments made at the first visit following Screening will be considered screening failures.

Only patients considered screening failures will be replaced.

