9.6 Prior and Concomitant Therapy

The following medications/therapies are prohibited during the study and within 28 days prior to Screening:

- Other investigational products
- Other systemic antitumor therapy.
- Local radiation therapy to any area except for the abdominal/retroperitoneal area including the kidney tumor is allowed. The impact of any palliative radiotherapy administered on evaluable lesions must be discussed with the Medical Monitor and documented in the eCRF

The following medications are prohibited within 7 days prior to Screening Visit until Nephrectomy:

- Systemic per oral corticosteroids exceeding 10 mg/day. However, inhaled, intranasal and local (per cutaneous) steroids for treatment of skin disorders, chronic obstructive lung disease, asthma, or allergy are acceptable irrespective of dose.

Specific instructions in relation to the nephrectomy and Intuvax vaccinations:

- Concomitant oral antithrombotic, e.g. acetylsalicylic acid (ASA), withdrawal and restart to be done according to local practice in connection with the nephrectomy and according to local practice for invasive examinations in connection with Intuvax vaccinations.
- Anticoagulants, local practice applies for start and stop of anticoagulant treatment and shift to/use of low molecular weight heparin treatment in connection with

nephrectomy and according to local practice for invasive examinations in connection with Intuvax vaccinations

Medication, which is considered necessary for the patient's safety and well-being, may be given at the discretion of the Investigator as per local guidelines and Standard of Care. Whenever there is a medication available to prevent or alleviate a symptom it will be offered to the patient.

Patients who respond inadequately to sunitinib treatment and need to change systemic anti-cancer therapy should be scheduled for an End-of-Study Visit before being withdrawn from the study, *Section 8.5*. As described in *Section 11.2* safety evaluation must also be performed up to 30 days after the patient's last dose of IMP administered in the study.

The use of all medication by the patient must be recorded in the eCRF, *Section 10.4.4*.

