6.3.6 Secondary Efficacy Analyses

PFS from start of sunitinib according to RECIST 1.1

PFS from start of sunitinib treatment will be derived as date whichever occurred first of any cause of death or date for first tumor progression (which is date for centrally assessed CT performed, according to RECIST 1.1) minus date for start of sunitinib treatment plus 1 day.

For the analysis of PFS only deaths occurring before end-of-trial will be accounted for in the analysis.

Analysis of PFS will be evaluated the following way:

Survival functions will be displayed graphically using Kaplan-Meier plots, and life table statistics will be produced including summaries of number of events and censored observations. Estimates of cumulative 25%, 50% (median) and 75% percentiles of survival with corresponding 95% confidence intervals will be calculated.

Comparison between Intuvax+sunitinib, vs. sunitinib alone will be done using a stratified log-rank test (controlling for strata intermediate/high risk), separate analyses will also be done by strata.

With protocol versions before version 4.0, intermediate risk patients did not have to initiate treatment with sunitinib at a fixed time point according to the visit schedule. Consequently some patients were never started on sunitinib, and in some cases sunitinib treatment was initiated at a later time point. The sunitinib start date constitutes the baseline time point for PFS according to protocol version 4.0 and after. In the analyses, patients who either had a delay or never started sunitinib will be included under the assumption that sunitinib treatment would have been initiated according to the final design, the date of the visit following the nephrectomy visit will be used as baseline.

Another issue that will be considered in the analysis is that some patients may have been discontinued based on general clinical disease progression as evaluated by investigator from symptoms/signs of disease, rather than based on a PD according to RECIST 1.1. For the analysis such cases will be handled strictly based on the RECIST 1.1 evaluation, thus if a patient is withdrawn without a CT confirmed PD the subject will be censored at last CT

Analyses will be based on FAS and repeated for separately by strata..

Proportion of Objective Response Rate (ORR) and Disease Control Rate (DCR) from start of sunitinib

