As the technology used by [REDACTED] eliminates much more the subjective measurement of CD8+ infiltration and has been technically validated, the [REDACTED] approach is widely regarded as the more accepted one in contrast to the [REDACTED] approach. Additionally, issues in the quality of the execution had been identified in the beginning of the

[REDACTED]

[REDACTED]

[REDACTED]

Evaluation of auto- and allo-immunization parameters

Auto- and alloimmunization parameters will be assessed prior to vaccination at Vacc1 Visit and at Sun-Start Visit for patients randomized to Intuvax.

Autoimmunization parameters, anti-nuclear antibodies (IF-ANA), anti-mitochondrial and anti-liver-kidney icrosomal antigens will be assessed as “Negative” or “Positive” and additional assessment of “Weak” or “Strong” will be done for positive results on Homogenous, Speckled, Nucleolar, and Centromere patterns.

Alloimmunization at the humoral level by screening of alloantibodies against HLA-A, B, C (HLA class I) and HLADR, DQ, DP (HLA class II) antigens will be assessed as “Present” or “Not Present”.

The results of auto- and allo-immunization parameters will be tabulated using general summary statistics for categorical data. In addition shift tables will be presented to summarise the changes from the assessment prior to vaccination 1, to the Sun-start visit.

TTF defined as progressing during or after treatment with Intuvax+sunitinib or sunitinib followed by the start of subsequent second line systemic therapy

TTF is defined as progressing during or after treatment with Sunitinib or Intuvax + Sunitinib followed by the start of subsequent second line systemic therapy including immune checkpoint inhibition or tyrosine kinase inhibition, and will be derived as the date of screening until start date of second line treatment following progression. Similar censoring rules as applied for PFS will be used. Patients with PD without any second line treatment will be censored at withdrawal. Similar survival statistics as applied for analysis of PFS will be conducted.

Association between Sunitinib dose density and primary and secondary endpoints

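### Time to treatment failure censors progressed patients at withdrawal unless second-line therapy has started, so failures are censored at about the moment they occur and TTF is overstated

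*SAP*

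**What the plan says.** The TTF paragraph in SAP section 6.3 describes failure as progression followed by second-line systemic therapy. The time "will be derived as the date of screening until start date of second line treatment following progression". Two censoring statements follow: "Similar censoring rules as applied for PFS will be used", and then "Patients with PD without any second line treatment will be censored at withdrawal".

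The PFS rule that TTF borrows (SAP 6.3.6) concerns patients discontinued on clinical progression: "thus if a patient is withdrawn without a CT confirmed PD the subject will be censored at last CT".

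The protocol fixes what happens at progression:

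- Section 7.2.1.6: "In case of PD this visit should be considered the End-of-Study Visit".
- Section 8.5 lists progressive disease (PD) on sunitinib as a reason for withdrawal. At withdrawal the reason and date are recorded, and "subsequent planned replacement therapy will be documented in the electronic case report form (eCRF").
- Section 9.6 includes "Other systemic antitumor therapy" among the therapies prohibited during the study. It says that patients who respond inadequately and "need to change systemic anti-cancer therapy should be scheduled for an End-of-Study Visit before being withdrawn from the study".

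SAP Appendix 1 plans life tables, quartiles and a log-rank test for TTF (Tables 14.2.29 to 14.2.31) and a Kaplan-Meier figure (14.2.38).

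**The concern.** Kaplan-Meier and log-rank methods assume that a patient censored at time t has the same future risk of the event as a similar patient still under observation. Here the reason for censoring is the failure itself. A patient whose disease progresses on sunitinib leaves the study at that point and is treated as failure-free, unless a second-line start is on file. Those too ill for further therapy, or who die first, have failed most clearly, yet under the rule progression alone never makes them an event.

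A reader of the TTF tables will take the estimate as the time until treatment failed. Under this rule it is longer than that. In an open-label trial, later therapy may also be given or recorded differently in the two arms, and the comparison would then partly reflect that difference.

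**Working it through.** The documents give no expected TTF, event count or power, so there is no planned figure to reproduce. The check has two parts.

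**1. Tracing a patient through the rules.**

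- *RECIST progression, no second-line therapy ever given.* The PD visit is the End-of-Study Visit, so withdrawal is at or about PD. TTF is censored there. This holds whatever data are collected.
- *RECIST progression, second-line therapy after exit, start date not on file.* Same result.
- *RECIST progression, second-line therapy after exit, start date on file.* Counted as an event.
- *Clinical progression without CT-confirmed PD.* Under the borrowed PFS rule, censored at the last CT, which is before the failure.
- *Death before second-line therapy.* Not addressed. In PFS death is an event, but TTF borrows the censoring rules and names only the second-line start as its event.

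The schedule acts on locally verified PD (Protocol 7.2.1.6), whereas Protocol 10.4.3 bases TTF on central assessment. The SAP does not say which PD triggers the TTF rule.

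**2. Size, under stated assumptions.** Let progression have constant hazard λ and true median m, so λ = ln 2 / m. Let p be the share of progressed patients with a recorded second-line start at about the time of PD. The other 1 − p are censored at PD. The hazard that the analysis sees is pλ, so

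- estimated median = ln 2 / (pλ) = m / p;
- estimated failure-free share at 18 months = exp(−18pλ);
- expected events by 18 months among 90 patients = 90 × (1 − 0.5^(18/m)) × p.

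The 90 patients and the 78 weeks on study (about 18 months) come from the documents. The values m = 9 months and all p are assumed for illustration. With m = 9, the 18-month share is 0.5^(2p) and expected events are 90 × 0.75 × p = 67.5p.

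| p | Median (months) | Failure-free at 18 months | Events |
|---|---|---|---|
| 1 (every progression counted) | 9.0 | 25% | 68 |
| 0.7 | 12.9 | 0.5^1.4 = 38% | 47 |
| 0.5 | 18.0 | 0.5^1.0 = 50% | 34 |
| 0.3 | 30.0 (not reached by 18) | 0.5^0.6 = 66% | 20 |

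With m = 6 the median becomes 6/0.7 = 8.6 and 6/0.5 = 12.0 months. A large-sample simulation with an 18-month cut-off agreed with these medians.

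**Between-arm comparison.** With the same λ in both arms, the apparent hazard ratio is p(vaccine)/p(control). Simulation of 4,000 trials of 60 vs 30 patients (90 at 2:1), with m = 9, an 18-month cut-off, an unstratified log-rank test and |z| > 1.96, gave:

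| p vaccine | p control | Apparent HR | Rejection with no true effect |
|---|---|---|---|
| 0.7 | 0.7 | 1.00 | 5% |
| 0.6 | 0.8 | 0.75 | 18% |
| 0.5 | 0.8 | 0.62 | 31% |
| 0.4 | 0.8 | 0.50 | 56% |
| 0.8 | 0.5 | 1.60 | 28% |

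**The case against.** The SAP defines the endpoint openly as progression followed by second-line therapy, and progression is already an event in PFS and TTP. TTF is outside the listed primary and secondary endpoints, and all testing is exploratory and unadjusted (SAP 6.4). One can argue that a better label would do. That stands in part: renaming is one acceptable remedy, and the point is modest. It does not rescue the present name or the censoring at withdrawal.

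Three stronger readings are tempting, and the documents do not support them.

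- *The trial cannot see second-line starts.* The readable text shows no explicit route for collecting an actual start date after exit. However, Protocol 9.6 requires all medication used by the patient to be entered in the eCRF, Protocol 10.4.4 includes start dates, and the sections on the further endpoints are redacted. A route may exist, and none is asserted to be missing. Patients who never receive second-line therapy are censored either way.
- *The log-rank test only compares how many second-line starts are on file.* With equal p in both arms it keeps its 5% level. Bias needs uptake or recording to differ by arm. An open-label design permits this, but nothing in the documents shows it.
- *OS becomes hard to interpret.* OS runs from randomization to death from any cause and does not use the TTF rule.

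**Conclusion.** The point holds for TTF. Followed as written, the rule censors informatively at or about failure, overstates TTF and loses events. Under a constant hazard, with recorded second-line starts close to PD, the median is inflated by 1/p. The illustrative 9 months becomes 12.9 at p = 0.7 and 18 at p = 0.5, while expected events fall from about 68 to 47 and 34. The values of m and p are assumptions, and the actual p cannot be found from the documents. Bias in the treatment comparison is conditional on p differing between arms. OS, 18-month survival and PFS are unaffected. The change should be made because it is cheap and the endpoint as named would mislead, but no primary or listed secondary conclusion depends on it.

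**What to change.** In the TTF paragraph of SAP section 6.3:

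1. Define the event as the earliest of progression (RECIST or clinical, as already used for TTP), recorded discontinuation of sunitinib for lack of effect, recorded start of new systemic anticancer therapy, or death.
2. Delete the rule that censors patients with PD at withdrawal.
3. Censor only patients with none of these events, and do not import the PFS rule for clinical progression without CT-confirmed PD.

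The trial already handles dates for progression, withdrawal, sunitinib exposure and death. The start of new therapy counts where it is recorded, and the definition no longer depends on it.

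Alternatively, keep the present event, rename the endpoint *time to second-line therapy*, and treat death without second-line therapy explicitly as an event or a competing risk. Collecting the first subsequent therapy and its start date on the survival report form would support this option. It is optional and needs a data-flow change, because Protocol 11.3 sends that form to the safety database only.

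Cost: SAP wording and reprogramming of three tables and one figure. The downside of the first option is that TTF moves closer to PFS and its values become shorter. Neither option changes how patients are managed.
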